**Title:** Effect of Topical Chylobinoid Cream on Pain and Function Scores for Hallux Disorders: A Randomized Controlled Trial

**Purpose:** The purpose of this study is to compare the change in pain scores in patients with hallux rigidus and hallux valgus who are treated with topical cannabidiol cream vs. placebo.

**Hypothesis:** Patients treated with topical 1.5% chylobinoid cream (chylobinoid is approximately 85% magnesium-cannabidiolic acid or Mg-CBDa, 5% CBD, 5% other cannabinoids, and naturally occurring plant lipids in a neutral emollient) will show improvement in hallux pain compared to those patients treated with placebo.

# **Background:**

Conditions affecting the first metatarsophalangeal (MTP) joint are highly prevalent and make up a significant portion of orthopedic foot and ankle clinic visits. Hallux rigidus, Latin for "stiff toe," is the term for osteoarthritis of the first MTP joint. It is the most common form of foot arthritis, and incidence continues to rise as the population ages. Hallux valgus is a common foot deformity characterized by chronic subluxation of the first MTP joint, with lateral deviation of the proximal phalanx and medial deviation of the first metatarsal. These conditions represent a large portion of chronic forefoot disorders.

Both of these chronic conditions are associated with pain, inflammation, functional impairment, and corresponding radiographic changes. While operative interventions exist, nonoperative modalities are the mainstay of treatment for most patients. Options include shoe wear modification, manual and physical therapy, intraarticular injection of corticosteroids or sodium hyaluronate, oral nonsteroidal anti-inflammatories, and foot orthoses. Oral anti-inflammatories are some of the most effective non-operative strategies, but unfortunately are associated with major adverse side effects and are contraindicated in many patients. Although these medications do not alter the underlying deformity, they are an important, cost-effective, and clinically validated tools in the management of hallux valgus and hallux rigidus. Oral non-steroidal anti-inflammatories (NSAIDs) are contraindicated in many patients with certain gastrointestinal, renal, or cardiac disease.

The endocannabinoid system has been shown to play an important role in inflammatory regulation, and pain perception. Cannabidiol (CBD) is a component of the cannabis plant that is responsible for the signaling mechanism of cannabinoid receptions involved in a variety of pain pathways. CBD has been found to suppress progression of arthritis by suppressing the inflammatory cytokine pathway involved in osteoarthritis. It has been found to reduce synovitis and decrease progression and pain secondary to osteoarthritis. Philpott et al. assessed pain behavior and joint afferent mechanosensitivity in rats with collagen-induced osteoarthritis of the knee. They found that CBD infusion decreased joint inflammation, inhibited mechanosensitivity of joint nociceptors, and improved hind limb weight bearing and limb withdrawal threshold. Transdermal CBD was found to reduce joint swelling, immune cell infiltration, and synovial thickening in a dose-

dependent manner in rats with induced knee arthritis. This and other studies show preliminary evidence that CBD is a safe, effective way to improve pain and functional impairment associated with osteoarthritis.

CBD and its more active form, CBDA, have been studied since the 1960s, and different formulations and administrations have been shown to treat a wide variety of pathology. In the 1970s, publications on the compound increased after research found antiepileptic effects with systemic administration. Recent studies have focused on anti-inflammatory and antioxidative effects after both IV and topical administration. Studies have evaluated oral CBD for pain in patients with kidney disease, multiple sclerosis, spinal cord injury, brachial plexus injury, and limb amputation. CBD has been found to decrease generalized pain and increase function after short term.

Topical use for orthopedic disorders has yet to be studied, although the available literature shows that topical CBD application has therapeutic potential for relief of arthritis pain-related behaviors and inflammation without evidence side effects. More recently, a topical chylobinoid cream formulation has become available for study. Chylobinoid describes a chylomicron-like complex extracted from raw hemp flower utilizing a proprietary mineral infusion process developed by Synthonics, Inc. that consists of approximately 85% magnesium-cannabidiolic acid or Mg-CBDa, 5% CBD, 5% other cannabinoids, and naturally occurring plant lipids.

This study would be the first prospective randomized controlled trial to evaluate the use of topical chylobinoid cream in the treatment of hallux rigidus and hallux valgus. It has the potential to improve pain and function for patients who suffer from moderate to severe hallux pain, with low cost and minimal side effects. Additionally, it may significantly reduce the concurrent need for narcotics, NSAIDs, corticosteroids and other oral/topical analgesic remedies.

**Study design:** Prospective randomized controlled trial

#### **Inclusion criteria:**

- Patients with new diagnosis of hallux rigidus and hallux valgus
- VAS pain score of 4 or higher
- Age > 18 years
- Patient provides informed consent

#### **Exclusion criteria:**

- Previous operative procedure to the first metatarsal for treatment of hallux valgus or hallux rigidus
- VAS pain score at presentation less than 4
- Concomitant hallux valgus and hallux rigidus on the ipsilateral side
- Allergy to CBD, CBDa or any other ingredient contained in the topical cream
- Pregnant patients
- Non-English speaking patients

- Patient is incarcerated, incapacitated, or otherwise unable to provide appropriate informed consent

# Patients and protocols:

Patients will be recruited from the practices of a fellowship trained Orthopedic Foot and Ankle surgeon at Rush University Medical Center. Patients with a new diagnosis of hallux valgus or hallux rigidus without prior operative intervention on the first metatarsal will be approached for enrollment in the study. Pre-treatment VAS pain scores and the Foot Function Index (FFI) are collected as a routine question on new patient questionnaires. Patient's with a VAS pain score of < 4 will be excluded. The goal of the intervention is to improve pain, and patient's with minimal pain at presentation have a little possibility of showing therapeutic response.

Enrolled patients will be randomized to receive chylobinoid cream vs. placebo cream (neutral emollient containing no active agent) for topical treatment of hallux rigidus or hallux valgus. Patients and treating physician will be blinded to the intervention. Patients will not be charged nor will their insurance be billed for cost of the chylobinoid cream or placebo cream. Patients will be instructed to apply the topical cream as needed for pain for a total duration of four weeks. This topical treatment will be combined with other commonly employed conservative modalities, including physical therapy and orthotics as clinically indicated. Patient's will receive the FFI survey via email weekly for a total of 4 weeks after treatment initiation. Patient's will be instructed to keep track of daily VAS pain scores in a pain journal for the four weeks of treatment.

Patient's will attend their regularly scheduled four weeks follow up clinic visit. Post-treatment VAS pain score will be collected at that visit, along with their daily pain journal. Patients will fill out a brief survey regarding their experience with the treatment. The remaining chylobinoid cream will be collected from patients and weighed in order to assess the amount of product used during the four-week study period. The difference in pre and post-treatment VAS score and FFI will be determined between the chylobinoid and placebo groups.

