### Sample Size:

Power analysis was preformed using a retrospective review of internal patients with new hallux rigidus and hallux valgus diagnoses. VAS scores at the time of presentation were determined. VAS score at presentation for hallux rigidus was 6.74 with standard deviation of 1.7. VAS score at presentation for hallux valgus was 6.45 with standard deviation of 1.68. A clinically significant improvement in VAS pain score was defined as a 2-point decrease. Power analysis based on 80% power and alpha of .05 for detection of a 2-point decrease in VAS score determined the study would require 12 patients with hallux rigidus per group (24 total) and 12 patients with hallux valgus per group (24 total). In order to account for 20% loss to follow up, a total of 28 patients will be enrolled for each hallux rigidus and hallux valgus group (56 total patients for the entire study).

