### **Demographics/patient specifics:**

Age, sex, medical co-morbidities, weight, height, pre-treatment pain scores, BMI

**Primary outcome measure:** Post-treatment VAS score averaged daily over 4 weeks.

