### **Secondary outcome measures:**

- 1. Pre- to post-treatment difference in VAS score
- 2. Pre- to post-treatment difference in FFI
- 3. Post-treatment FFI at different time points (1, 2, 3, and 4 weeks post treatment)
- 4. Adherence to treatment
- 5. Amount of Chylobinoid cream vs. Placebo cream used during the study period
- 6. Do you believe you received the treatment or placebo? (4 weeks)
- 7. Did the cream we gave you help with your pain? (4 weeks)

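### Does naming only chylobinoid cream in the weighing sentence leave placebo use unmeasured?

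*Protocol*

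**What the plan says.** Under Patients and protocols, patients are randomized to one of two creams and use it at their own discretion: "Patients will be instructed to apply the topical cream as needed for pain for a total duration of four weeks". On masking, the same section states: "Patients and treating physician will be blinded to the intervention". At the four-week visit the unused cream is dealt with in one sentence: "The remaining chylobinoid cream will be collected from patients and weighed in order to assess the amount of product used". The sentence after it turns to the comparison of the two groups on VAS and FFI.

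Under Secondary outcome measures, item 5 reads: "Amount of Chylobinoid cream vs. Placebo cream used during the study period". Item 4 is adherence, for which no separate measurement is described. The pain journal is described as holding daily VAS scores, and the closing survey as covering patients' experience; neither is said to record quantity used.

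The primary outcome is defined as "Post-treatment VAS score averaged daily over 4 weeks".

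**The concern.** The weighing sentence names the active product, and elsewhere in the same section that name denotes one arm as opposed to the other. Item 5 is a contrast between arms. If the sentence were carried out exactly as written, there would be weights for the chylobinoid arm and none for the placebo arm, and item 5 could not be computed.

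Three features make this look worth raising:

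- Use is as needed, so each patient sets the exposure, and it may differ between arms. The quantity used helps a reader interpret the pain results.
- Returned weight is the only measure of quantity that the Protocol describes.
- A container not collected at the four-week visit is unlikely to be recovered, and no later analysis decision can replace a weight that was never taken.

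A rule that collected cream from one arm only would also require someone at the visit to know the allocation.

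**Working it through.** The Protocol states no figure on this point, so there is none to reproduce. The check is a comparison of texts, followed by a count of what the literal reading would cost.

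**Texts side by side**

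| Place in the Protocol | What it implies about placebo cream |
|---|---|
| Patients and protocols, weighing sentence | Names chylobinoid only, but the return is from patients in general and its purpose is the amount of product used |
| Patients and protocols, next sentence | Compares the chylobinoid and placebo groups |
| Patients and protocols, blinding sentence | Patients and treating physician do not know the arm, so they cannot apply a return rule that depends on it |
| Secondary outcome measures, item 5 | Requires a quantity used for placebo as well as chylobinoid |

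Four considerations favour collection from both arms: item 5, the unrestricted return from patients, the generic purpose of the weighing, and the blinding. One favours collection from a single arm: the product name in one sentence. No section describes an unblinded person at the visit who could pick out the chylobinoid patients. A one-arm return would also signal to patients which cream they had, just when they are asked to guess their treatment (secondary outcome 6).

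**How much weight the single noun can bear.** The Protocol is loose with terms elsewhere. The Purpose speaks of cannabidiol cream where the Hypothesis speaks of chylobinoid cream. The Inclusion criteria join the two diagnoses with *and*, although the Exclusion criteria rule out both on the same side and Patients and protocols uses *or*. A non-generic noun in this document is weak evidence of a deliberate one-arm procedure.

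**Cost under the literal reading**

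Inputs from Sample Size: 56 patients enrolled, 28 per diagnosis; 20% loss to follow-up; 12 evaluable per group in each diagnosis. Equal allocation is assumed, as the equal numbers per group suggest.

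- Placebo patients enrolled: 56 / 2 = 28.
- Placebo patients returning after 20% loss: 28 × 0.80 = 22.4, about 22.
- Planned evaluable placebo patients: 12 + 12 = 24, inside that range.

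So 22 to 28 containers would go unweighed. Item 5 would then be lost altogether as a comparison between arms, since one side would be empty.

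**Cost under the reading that fits the document.** Cream is returned and weighed in both arms, no container is missed, and item 5 is computed as listed. Correcting the noun would alter no datum and no result.

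**The case for a change.** The strongest case for a change rests on the section's own usage. When it means both creams, it names both (in the statement on charges) or uses a neutral term (in the instruction to apply). Only the weighing sentence names the active product alone, so staff who followed it to the letter would not be misreading it. Collection is a site procedure that a statistical analysis plan cannot supply afterwards. The correction costs a few words at a visit that already takes place, against a loss that could not be repaired. On this view, having to infer a procedure from the outcome list is itself the defect.

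Part of this stands. The mismatch is in the text, and it is true that an SAP could not restore missing weights. What does not stand is the step from an inconsistent noun to a likely loss of data. The letter of the sentence cannot be followed by blinded staff, and no other part of the Protocol equips anyone to follow it. The inference asked of the reader is short, because item 5 names both creams.

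The argument could be widened by asking for the dispensed weight to be recorded, for the subtraction to be written out, and for weighing without knowledge of allocation. Measuring use from what is left already implies a known starting weight, and the rest is operational detail that a site settles in its working procedures. The Protocol states nothing wrong on these points.

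The appeal to reading pain results against use is also limited, because the Protocol lists no analysis that relates pain to quantity used. A link between returned weight and the adherence outcome is plausible, but it is an inference and not something the document states.

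**Conclusion.** The concern does not call for a change to the plan. The weighing sentence and secondary outcome 5 are worded inconsistently, and the cause is almost certainly a slip: the active product's name was written where the study cream was meant. The outcome list and the blinded design make the intended procedure clear, and anyone running the visit would collect cream from both arms.

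The expected effect on results is nil. The largest conceivable effect is the loss of secondary outcome 5 through 22 to 28 unweighed placebo containers, and it requires a one-arm procedure that the Protocol gives blinded staff no means of carrying out. The primary outcome would be untouched even then, since it is built from VAS scores alone.

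This conclusion rests on two assumptions: allocation is equal, which affects only the count of containers, and the four-week visit is conducted by people blinded to arm or acting as if they were. If the document is revised for other reasons, a neutral term for the cream would tidy the sentence, but nothing in the analysis depends on it.

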### Sample Size:

Power analysis was preformed using a retrospective review of internal patients with new hallux rigidus and hallux valgus diagnoses. VAS scores at the time of presentation were determined. VAS score at presentation for hallux rigidus was 6.74 with standard deviation of 1.7. VAS score at presentation for hallux valgus was 6.45 with standard deviation of 1.68. A clinically significant improvement in VAS pain score was defined as a 2-point decrease. Power analysis based on 80% power and alpha of .05 for detection of a 2-point decrease in VAS score determined the study would require 12 patients with hallux rigidus per group (24 total) and 12 patients with hallux valgus per group (24 total). In order to account for 20% loss to follow up, a total of 28 patients will be enrolled for each hallux rigidus and hallux valgus group (56 total patients for the entire study).

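### Enrolling 28 patients per diagnosis covers about 14% loss to follow-up, not the stated 20%; keeping 12 per arm at 20% loss would take 30 per diagnosis

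*Protocol*

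**What the plan says.** The Sample Size section of the Protocol gives the design inputs: "Power analysis based on 80% power and alpha of .05", "for detection of a 2-point decrease in VAS score", and a standard deviation at presentation for each diagnosis (1.7 for hallux rigidus, 1.68 for hallux valgus). From these it concludes that the study "would require 12 patients with hallux rigidus per group (24 total) and 12 patients with hallux valgus per group (24 total"). The next sentence inflates that requirement: "In order to account for 20% loss to follow up, a total of 28 patients will be enrolled" in each of the two diagnoses, with 56 given as the study total.

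Two other places bear on the consequence. Under Patients and protocols, the planned comparison is worded without reference to diagnosis: "The difference in pre and post-treatment VAS score and FFI will be determined between the chylobinoid and placebo groups". The primary outcome is "Post-treatment VAS score averaged daily over 4 weeks", a different quantity from the single score at presentation whose standard deviation was used.

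**The concern.** A loss allowance is meant to ensure that, if the stated fraction of patients drops out, the required number remains. Here 24 are required per diagnosis and 28 are enrolled, a margin of 4, while 20% of 28 is 5.6. The margin is therefore smaller than the loss it is said to absorb.

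The sizing is done separately in each diagnosis, and 12 per arm only just meets 80% power, so there is little slack. Anyone relying on this section, including an ethics committee or someone monitoring retention, would believe that each cohort tolerates 20% loss when it tolerates about 14%. A cohort that loses exactly the allowed fraction ends below the size the plan says it needs.

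**Working it through.** **Inputs, all from the Sample Size section:** alpha 0.05; power 80%; difference 2 VAS points; SD 1.70 (rigidus) and 1.68 (valgus); 12 per arm and 24 per diagnosis evaluable; 20% loss; 28 enrolled per diagnosis, 56 overall. Not stated, and assumed here: two-sided testing, and that the 2 points are a difference between arms.

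**Step 1: reproduce the 12 per arm.** Normal formula, n per arm = 2(z₁₋α/₂ + z₁₋β)² SD² / δ².

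- Rigidus: 2 × (1.960 + 0.842)² × 1.70² / 2² = 11.34, rounded up to 12.
- Valgus: 2 × (1.960 + 0.842)² × 1.68² / 2² = 11.08, rounded up to 12.

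The stated figure reproduces. A one-sided test (1.645 in place of 1.960) gives 8.93 and 8.72, hence 9, so two-sided is the reading that fits.

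**Step 2: check the inflation.** This step uses only 24, 20% and 28.

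- Completers at 20% loss: 28 × 0.8 = 22.4 per diagnosis, or 11.2 per arm; 56 × 0.8 = 44.8 overall, against 48 required.
- Tolerable loss: 28 − 24 = 4, and 4/28 = 14.3%.
- Enrolment needed: 24/(1 − 0.20) = 30 per diagnosis, 60 overall.
- The cruder rule of adding 20%: 24 × 1.2 = 28.8, also above 28.
- A route that does give 28: 12 × 1.2 = 14.4 per arm, rounded down to 14, doubled.

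**Step 3: effect on power within a diagnosis.** Normal formula: power = Φ(δ / (SD√(2/n)) − 1.960). The t-test column uses the noncentral t distribution.

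| n per arm | Normal, rigidus / valgus | t-test, rigidus / valgus |
|---|---|---|
| 12 (required) | 82.2% / 83.0% | 78.6% / 79.6% |
| 11.2 (average left at 20% loss) | 79.5% / 80.4% | 75.5% / 76.5% |
| 11 | 78.8% / 79.7% | 74.7% / 75.7% |

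Within either method, the drop from 12 per arm is about 2.6 to 4 percentage points.

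**Step 4: pooled reading.** With both diagnoses together, 44.8/2 = 22.4 per arm remain. Power is 97.6% / 97.9% (normal) or 97.1% / 97.3% (t-test) at SD 1.70 / 1.68.

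**Step 5: sensitivity to the SD.** The SD of the four-week daily average is not given. At 11 per arm, normal-formula power would be 91.8% with an assumed SD of 1.4 and 65.0% with an assumed SD of 2.0. The absolute power figures are therefore only indicative. Step 2 does not depend on the SD.

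**Step 6: chance of ending short.** If each patient independently has a 20% chance of being lost (an illustrative assumption), a cohort of 28 keeps at least 24 with probability 0.31, and a cohort of 30 with probability 0.61.

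**The case against.** The best case on the other side is that this is a very small slip. It amounts to 2 patients per diagnosis and looks like a rounding choice: on the per-arm route the gap is 0.4 of a patient. By the formula that reproduces the plan's own 12 per arm, power at 20% loss is 79.5% and 80.4%, essentially the target. If the trial is analysed with the diagnoses pooled, which the Patients and protocols section permits as a reading, power is ample either way. The lower t-test figures should not all be put down to dropout, because by that method 12 per arm already gives 78.6% and 79.6% with nobody lost. Finally, 20% is an allowance and not a forecast.

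Most of this stands, and it limits the weight of the point. It does not make the sentence correct. Adding 20% is not the inflation that offsets a 20% loss, and a requirement should not be rounded down. Nothing elsewhere in the Protocol repairs the figure. A separate analysis plan could not repair it either, because the enrolment target and the allowance are both fixed here.

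**Conclusion.** The concern holds. On the Protocol's own numbers, 28 per diagnosis covers 14.3% loss, not 20%. The shortfall is 2 enrolled patients per diagnosis and 4 overall (56 against 60). This rests on no assumption beyond the stated 24, 20% and 28.

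The consequence is modest: a few points of power in the diagnosis-specific comparisons, leaving them at or slightly under 80% by the normal formula, and little of practical importance if the diagnoses are pooled. Those power statements do rest on assumptions: two-sided alpha 0.05, a 2-point difference between arms, and presentation SDs standing in for the unreported SD of the primary outcome. The point should be fixed because a stated planning figure is wrong; it does not show a seriously underpowered trial.

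**What to change.** Keep 56 patients and correct the sentence, for example:

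> Each diagnosis will enrol 28 patients (56 overall), which retains the required 24 with up to about 14% lost to follow-up. At 20% loss about 11 per arm would remain in each diagnosis. Power for a 2-point difference between arms at two-sided alpha 0.05 would then be about 79–80% by the normal approximation, or 75–76% by a t-test (79–80% by t-test with no loss). These figures use the standard deviations at presentation, 1.70 and 1.68.

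A shorter version that gives only the 14% would also cure the arithmetic. If the investigators prefer to keep the 20% allowance and the 12 per arm, the enrolment that delivers both is 30 per diagnosis, 60 overall.

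The first option costs one sentence and no extra patients; its downside is that the stated allowance and power look slightly less favourable. The second costs 4 more patients.
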